#### 2. STUDY DESIGN

#### 2.1 INCLUSION AND EXCLUSION CRITERIA

#### Inclusion criteria:

- Patients' data entries from ISAR who are from countries that have at least two biologics available (defined as the presence of a license for the treatment of severe asthma),
- Patients, 18 years of age or older, with a diagnosis of severe asthma which requires treatment with guideline-suggested medications with 2018 GINA:

Study Protocol: [OPCG-2005] Biologic Usage Patterns, Clinical Outcomes and Healthcare Resource Utilization (CLEAR)

- Treatment Step 4 and being uncontrolled OR
- Treatment Step 5.
- Registry data for a minimum of one year prior to index date (defined as the date of biologic initiation for biologic patients and date of ISAR enrolment for non-biologic patients) and 24 weeks after therapy or enrolment,
- Data received by ISAR before July 2021

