#### Initiated

- Continued: use of first biologic for at least 6 months, without indication of stopping or switching
- **Switched**: stopped the initial biologic and received a (one or more) different biologic, without restriction of any time lapse between biologics
- **Stopped**: stopped the initial biologic and did not receive another biologic. Caution will be taken as stoppers maybe on the path to switchers. Therefore, data will be reviewed to add a feasible follow-up time post stopping and free of not starting another biologic to ascertain true stoppers.

Study Protocol: [OPCG-2005] Biologic Usage Patterns, Clinical Outcomes and Healthcare Resource Utilization (CLEAR)

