#### Did not initiate:

- Not eligible: Did not meet the criteria for eligibility of biologic therapy and did not initiate any therapy
- Eligible: Eligible for biologic therapy but did not initiate any biologic therapy
- A "frequent-eligibility" criterion of each biologic class will be used to assess eligibility. This
  criterion will be constructed using the results from the ISAR biologic availability survey and
  will be subject to confirmation from the ISAR scientific steering committee (see Table 1 for
  possible criteria per biologic class)

[figure not shown]

Table 1: Frequent-Eligibility Criteria per Biologic Class. Patients who did not initiate biologic therapy and are eligible will meet any of the three criteria for any of the three biologic groups.

	Anti-lgE	Anti-IL5/5R	Anti-IL4/13
Background therapy	Met via ISAR inclusion criteria		
Positive Allergen test	Yes, AND	N/A	N/A
IgE levels	≥ 30 IU/mL, AND	N/A	N/A
BEC	N/A	≥ 150 cells/µL with long- term OCS, OR ≥ 300 cells/µL without long-term OCS, AND	≥150 cells/µL with long-term OCS, OR ≥300 cells/µL without long-term OCS, OR
FeNO	N/A	N/A	≥25 ppb, AND
Exacerbation OR Iong-term OCS	Pre-therapy exacerbation (≥2) OR On long-term OCS	Pre-therapy exacerbation (≥2) OR On long-term OCS	Pre-therapy exacerbation (≥2) OR On long-term OCS

The ISAR enrolment date will mark the start of the outcome period for those who did not initiate biologics while for those who did the index date will be signified by the First Biologic Therapy Start Date. A minimum of 16-weeks of follow-up time post biologic initiation (outcome period) will be applied in alignment with the ERS recommendation for time of biologic response assessment [8]. This is also congruent with the methodology used in the ISAR research project 'Defining and Characterizing Responders to Biologic TrEAtment in Severe AsthMa Patients (BEAM).' To assess the impact of this design, the study will evaluate and report the number of patients that had three types of follow-up data: 1.) <24 weeks, 2.) > 24 weeks to 1-year 3.) >1-year.

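### The protocol states two incompatible minimum follow-up periods (24 and 16 weeks), and initiators still on their first biologic below 6 months have no group

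*Protocol*

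**What the plan says.** Three places in the protocol bear on how long a patient must be followed.

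- **Section 2.1, Inclusion criteria.** Patients need one year of registry data before the index date "and 24 weeks after therapy or enrolment". This covers initiators and non-initiators alike.
- **Section 2.2, text after Table 1.** "A minimum of 16-weeks of follow-up time post biologic initiation (outcome period) will be applied". The reason given is an ERS recommendation on when to assess response to a biologic, and consistency with another ISAR project. The same paragraph plans to report how many patients have each of "three types of follow-up data: 1.) <24 weeks, 2.) > 24 weeks to 1-year 3.) >1-year".
- **Section 2.2, Initiated.** Continued means "use of first biologic for at least 6 months, without indication of stopping or switching". Switched means "stopped the initial biologic and received a (one or more) different biologic, without restriction of any time lapse between biologics". Stopped means that the first biologic was stopped and no other was received, with the added remark that "data will be reviewed to add a feasible follow-up time post stopping".

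Section 1.2 gives five groups, of which only these three are open to initiators. Section 2.4 reports 3,532 eligible patients without saying which follow-up minimum was applied.

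**The concern.** An analyst building the cohort from section 2.1 excludes initiators with 16 to just under 24 weeks of follow-up. An analyst working from section 2.2 includes them. The protocol does not say which section governs.

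The group definitions add a second problem. A patient still on the first biologic who has not reached 6 months meets either entry rule but not the definition of Continued, and cannot be Switched or Stopped because nothing was stopped. A patient who stopped or switched in the same interval is classified. Whatever is lost therefore comes from one side of the stopped/switched versus continued comparison, the second set of results planned in section 4.2.

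The first set, initiators versus non-initiators, is exposed in another way. The 16-week rule refers to time after biologic initiation, so non-initiators have only the 24-week criterion.

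**Working it through.** No sample-size or power figure is involved. The check converts the durations to days and asks whether the definitions cover every included initiator.

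**Inputs**

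- Entry minimum, section 2.1: 24 × 7 = 168 days.
- Entry minimum, section 2.2: 16 × 7 = 112 days.
- Continued threshold, section 2.2: 6 months, taken as 26 × 7 = 182 days. The protocol does not convert months to days; 6 × 30 gives 180, and calendar half-years give 181 to 184.

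**Step 1: the entry rules.** 168 − 112 = 56 days, or 8 weeks. If 168 days is enforced, the 16-week rule excludes nobody and the lowest reporting band is empty. Planning that band only makes sense if patients below 24 weeks can be in the study, so the inclusion criterion cannot be read as silently overriding the 16-week rule. The bands also leave out a patient with exactly 24 weeks, since one is strictly below and the next strictly above.

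**Step 2: the unclassified window.** For someone still on the first biologic, time on drug equals follow-up, because the index date is the start of that biologic. The window runs from the entry minimum to the Continued threshold.

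| Entry rule | Window at 182 days | Range for 180 to 184 days |
|---|---|---|
| 24 weeks | 182 − 168 = 14 days (2 weeks) | 12 to 16 days |
| 16 weeks | 182 − 112 = 70 days (10 weeks) | 68 to 72 days |

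It is open under either rule.

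**Step 3: who falls into it.** Switched and Stopped both require a stop and set no minimum time on treatment. An included patient who stopped or switched before 6 months has a group; one who stayed on the drug and was observed for less than 6 months does not.

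**Step 4: number of patients.** Section 1 reports an ISAR split of 2,791 continued, 356 stopped and 384 switched. These sum to 3,531 and reproduce the stated 79%, 10% and 11%. Those patients all had at least 6 months of follow-up, so the split says nothing about shorter records. No follow-up distribution is given elsewhere, so the count inside either window cannot be derived.

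**Step 5: after the fix.** With the Continued threshold equal to the entry minimum, the window is 168 − 168 = 0 days, or 112 − 112 = 0.

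**The case against.** The strongest reply accepts the 16 versus 24 week conflict but holds that little follows from it. Most of its limits stand.

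- A reader might infer that 6 months is a third follow-up minimum and that the cohort is undefined. It is a time-on-drug definition for one group. The entry conflict is between 16 and 24 weeks only.
- A reader might infer that short-follow-up continuers are lost on a large scale. Under the 24-week rule the window is only about two weeks wide, and few patients may fall in it.
- A reader might infer that the comparison groups face no follow-up requirement. If 24 weeks governs, switchers and stoppers need 24 weeks of post-index data too, so the built-in difference in minimum follow-up is about two weeks. For stoppers, section 2.2 also foresees a post-stop observation period, of unstated length. The net direction and size of any follow-up difference are not shown.
- A reader might infer that the 16-week rule inflates annualised rates by half, since one event in the shortest record counts 24/16 = 1.5 times as much. That is arithmetic for one hypothetical patient. Patients without events contribute zero under either rule. With a constant event rate, shorter records add variance without shifting the expected rate. The first analysis listed for the primary outcome in section 4.2 is time to first exacerbation with censoring, which does not annualise.

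The reply does not remove the two entry rules, the empty band or the missing group. The study-design figure and feasibility diagram are not visible here and might carry a follow-up value, but that would not reconcile the text. Nor is this detail that a protocol may leave to an SAP: the protocol fixes both rules, and an SAP would have to contradict one.

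**Conclusion.** The point holds in two parts. First, sections 2.1 and 2.2 give incompatible entry rules, 8 weeks apart, and the shorter is worded for initiators only. This rests on the text alone. Second, initiators still on the first biologic below 6 months have no group, over a window of about 2 weeks under the 24-week rule or about 10 weeks under the 16-week rule, taking 6 months as 26 weeks. The loss is one-sided because, as written, only patients still on treatment can fall into the window.

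The documents support no statement about how many patients are affected or how far any hazard ratio or rate would move. The point should be settled before the cohort is drawn, but it is not a demonstrated bias of known size.

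**What to change.** Reconcile section 2.1 and both parts of section 2.2:

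1. State one minimum post-index follow-up for all five groups, for example the 24 weeks of the inclusion criterion. If another value is preferred, use it throughout.
2. Define Continued as still on the first biologic at that same minimum, keeping the condition that no stop or switch is recorded, so that no included initiator still on treatment is left without a group. With 24 weeks this shortens the present time-on-drug requirement by about two weeks, which should be acknowledged.
3. Align the reporting bands: with a 24-week minimum, 24 weeks (inclusive) to 1 year and over 1 year.
4. State which minimum produced the 3,532 in section 2.4, and recount if it differs from the one adopted.
5. If a sensitivity analysis uses the other minimum, move the Continued threshold with it. Otherwise a 16-week analysis with a 24-week threshold reopens an 8-week window.
6. When the post-stop observation period is fixed, say where stoppers who do not complete it are placed.

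The cost is a few wording changes and a re-run of the feasibility count. No new data are needed.

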**Figure 3 Study Design** 

Health outcomes, such as exacerbations, asthma control status, emergency room visits, hospital visits, OCS dose (rescue and long-term), as well as health resource utilization outcomes (hospital, emergency room visits and non-invasive and invasive ventilation)) will be assessed across biologic usage groups during the outcome period. In ISAR, data on the outcomes are collected as part of routine general health assessments in accordance with respiratory care guidelines and/or recommended medical practice guidelines.

[figure not shown]
# Optimum Patient Care Global Study Protocol: [OPCG-2005] Biologic Usage Patterns, Clinical Outcomes and Healthcare Resource Utilization (CLEAR)

[figure not shown]
#### 2.3 DATA SOURCE

The ISAR registry is a multi-country, multi-center, observational epidemiologic data repository with retrospective and prospective data of patients treated with 2018 Global Initiative for Asthma (GINA) Step 5 or uncontrolled on GINA Step 4 treatment regimens. ISAR holds standardized, patient-level, fully anonymized data for ~9,654² (as of November 2020) patients with severe asthma from 19 national registries (Argentina, Australia, Bulgaria, Canada, Colombia, Denmark, Greece, India, Ireland, Italy, Japan, Kuwait, Mexico, Saudi Arabia, South Korea, Spain, Taiwan, UAE, UK and United States). The data is collected specifically for severe asthma research. All data contributors enter data via electronic Case Report Forms (eCRF) on a web-based platform customized for real-life data collection or within specialized electronic medical records. The reason for either stopping or switching the first biologic is also collected, when applicable [4]. Patient recruitment started in December 2015 Ethical governance for ISAR is provided by The Anonymous Data Ethics Protocols and Transparency (ADEPT) committee, an independent body of experts and regulators commissioned by the Respiratory Effectiveness Group (REG). The registry's scientific merit is ensured by the ISAR steering committee (ISC) that is made up of 48 severe asthma specialist or database experts from 25 countries (http://isaregistries.org/)

<sup>2 This does not include the 671 patients from the Australian Severe Asthma Network that was received on the 1st of Dec. as it is undergoing data quality assessments at the moment.

#### 2.4 FEASIBILITY

Optimum Patient Care Global
Study Protocol: [OPCG-2005] Biologic Usage Patterns, Clinical Outcomes and (CLEAR)

The diagram above shows the feasibility for the CLEAR study. Overall, 3,532 patients were eligible for the study. Most of them had initiated biologics and continued on them.

[figure not shown]
# 3.STUDY VARIABLES AND STUDY OUTCOMES

Values captured closest to, and at/before index date of the following variables will be used to describe the biologic utilization groups (objective 1). Again, the index date refers to the date at which the initiation biologic was started or the date of ISAR enrolment for those who did not initiate any biologics.

#### 3.1 DEMOGRAPHIC AND CLINICAL VARIABLES

Table 2 Demographic and clinical features to be described in Phase I of the study

Patient attributes	
Age	Age in completed years.
Sex	Female or Male.
Body Mass Index (BMI)	The ratio of weight (kg) to squared height (m  ). Categorised as underweight (< 18.5 kg/m  ), normal weight ( $\geqslant$ 18.5 kg/m  and < 25 kg/m  ), overweight ( $\geqslant$ 25 kg/m  and < 30 kg/m  ) and obese ( $\geqslant$ 30 kg/m  ).
Age of Asthma Onset	Age in completed years or months (if less than 1 year) at which asthma symptoms began. Early onset: <18 years of age; late onset: ≥18 years of age.
Smoking Status	Categorised as non-smoker, current smoker or ex-smoker; las ever.
Diagnostic Measurements	
Blood eosinophil count	Count of blood eosinophils (cells/uL).
Blood IgE level	blood level IgE (kU/L).
Predicted FEV1	Predicted value of forced expiratory volume in the first second of expiration (L).
Pre-bronchodilator FEV1	Measured forced expiratory volume in the first second of expiration, before the use of a bronchodilator (L).

Post-bronchodilator FEV1	Measured forced expiratory volume in the first second of expiration, after the use of a bronchodilator (L).
Pre-bronchodilator FVC	Forced vital capacity, before the use of a bronchodilator (L).
Post-bronchodilator FVC	Forced vital capacity, after the use of a bronchodilator (L).
Pre-bronchodilator FEV1/FVC Ratio	Measured FEV1 as a ratio of measured FVC.
Post-bronchodilator FEV1/FVC Ratio	Measured FEV1 as a ratio of measured FVC.
Fractional exhaled nitric oxide (FENO) test	Measurements of fractional nitric oxide concentration in exhaled breath, measured in parts per billion (ppb) at a flow rate of 50mL/s.
Skin Prick Test	Positive skin prick test
Therapy	
Long-term OCS	Maintenance oral corticosteroids (OCS)
Anti-IgE	Prescription for Anti-Immunoglobulin E (Anti-IgE)
Anti-IL5	Prescription for Anti-Interleukin 5 (Anti-IL5/5R)
Anti-IL4/13	Prescription for Anti-IL4/13
SCS-related comorbidities	Number of comorbidities reported from the following list: Anxiety, Depression, Osteoporosis, Diabetes, Peptic Ulcer, Pneumonia, Obstructive Sleep Apnea, Renal Failure, Heart Failure, Myocardial Infarction, Thromboembolism, Pulmonary Embolism, Serious infection (one or more). Other comorbidities based on availability of data.
Non-SCS-related comorbidities	Number of comorbidities reported from the following list: Allergic Rhinitis, Chronic Rhinosinusitis, Eczema, Nasal Polyps, Cancer

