First the demographic and clinical characteristics as mentioned in section 3.1 will be described in detail per group. This will include describing proportions on patients from each group based on their biomarkers, long term OCS (LTOCS) use, baseline demographics such as those outlined in Section 3.1. Next, the significant difference in level of T2 phenotypes and demographic or clinical characteristics (section 3.1) across the five groups will be compared and tested for statistical significance via Chi-square tests for comparison of counts data, and t-test or one-way analysis of variance (ANOVA) for continuous variables. Where appropriate, McNemar tests, paired t-tests will be considered. Statistical significance will be defined as p <0.05. Stata version 14.2 (College Station, TX, USA) will be used to conduct all statistical analyses and data manipulations.

Additionally, comparisons will be made as follows:

Study Protocol: [OPCG-2005] Biologic Usage Patterns, Clinical Outcomes and Healthcare Resource Utilization (CLEAR)

- 1. Switch vs. continue
- 2. Stop vs. continue
- 3. Patient received biologics vs. eligible but did not receive biologics
- 4. Biologic eligible (biologic users+ non-users but who qualify) vs. not eligible.

#### 4.2 OBJECTIVE 2

As there are various factors underpinning the probability of not receiving, receiving, continuing, switching, or stopping a biologic, comparing the clinical outcomes set forth in section 3.2 will need careful consideration. One of the main confounders to consider is the availability and/or accessibility of multiple biologics in a country. Therefore, all countries included in the analysis of assessing the clinical outcomes across biological utilization groups will have at least 2 biologics available in the market (availability defined as licensed in the country) at the time of the patient's enrolment into ISAR (index date). There will be a cut-off date of 01 Jan 2014 for assessment of clinical outcomes to ensure the availability of drugs in the market.

Furthermore, according to the results of objective 1 (pre-therapy or baseline characteristics), before assessing for differences in the clinical outcomes across groups, baseline imbalance will be examined across groups and matched accordingly. Prior to this step, the clinical outcomes of each group will be described.

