# 11.APPENDICES

Table S1. Full list of ISAR 95 core variables

Category	Variable field name	Recorded units
	Highest blood eosinophil count within the past year	Decimal number
Blood/Sputum	Date of the highest blood eosinophil count within the past year	DD/MM/YYYY
	Was this the highest blood eosinophil count during an exacerbation event?	No/Yes
	The highest blood eosinophil count within the past year and not during exacerbation	Decimal number
	Date of highest blood eosinophil count within the past year and not during an exacerbation event	DD/MM/YYYY
	Current blood eosinophil count	Decimal number
	Date of current blood eosinophil count	DD/MM/YYYY
	The highest sputum eosinophil count within the past year (percentage)	Decimal number
	Date of the highest sputum eosinophil count within the past year	DD/MM/YYYY
	IgE count	Decimal number
	Chest CT scan	Normal/Abnormal/Not done
Diamagatica	Date of chest CT scan	DD/MM/YYYY
Diagnostics	Bone densitometry (DEXA)	No/Yes
	Date of bone densitometry (DEXA)	DD/MM/YYYY
	Pre-bronchodilator FEV₁	Decimal number
	Post-bronchodilator FEV₁	Decimal number
Lung function	Pre-bronchodilator FVC	Decimal number
Lang laneaon	Post-bronchodilator FVC	Decimal number
	Predicted FEV₁	Decimal number (auto- calculated)

	Pre-bronchodilator FEV₁ (% predicted)	Decimal number (auto- calculated)
	Post-bronchodilator FEV₁ (% predicted)	Decimal number (auto- calculated)
	Predicted FVC	Decimal number (auto- calculated)
	Pre-bronchodilator FVC (% predicted)	Decimal number (auto- calculated)
	Post-bronchodilator FVC (% predicted)	Decimal number (auto- calculated)
	FEV₁/FVC ratio pre-bronchodilator (%)	Decimal number (auto- calculated)
	FEV₁/FVC ratio post-bronchodilator (%)	Decimal number (auto- calculated)
	PC20 methacholine/histamine test	No/Yes
	Date of PC20 test	DD/MM/YYYY
	PC20 test result	Decimal number
	FeNO test	No/Yes
	Date of FeNO test	DD/MM/YYYY
	FeNO test result	Decimal number
Allergen testing	Environmental allergen test	Serum allergen test (CAP, ELISA, RAST)/SPT/not done
	Serum allergy test: Positive to perennial allergen	No/Yes
	Serum allergy test: Specify positive allergen and result	Dust mite (e.g. D. pteronyssinus)/grass mix/cat hair/mould mix/dog hair/Aspergillus/other (please specify)
	Date of serum allergy test	DD/MM/YYYY
	SPT: Positive to allergen	No/Yes
	SPT: Specify positive allergen and result	Grass mix/trees/weed mix/Aspergillus/mould mix/dust mite/food mix/animal mix/cat

		hair/dog hair/other (please specify)

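### Objective 1 tests FEV1 and FVC in litres without adjustment, so differences in sex, age and height can appear as, or hide, differences in lung function

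*Protocol*

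**What the plan says.** Table 2 in Section 3.1 defines pre-bronchodilator FEV1 as "Measured forced expiratory volume in the first second of expiration, before the use of a bronchodilator (L" and post-bronchodilator FEV1 as "Measured forced expiratory volume in the first second of expiration, after the use of a bronchodilator (L". FVC is given in the same unit: "Forced vital capacity, before the use of a bronchodilator (L", with a matching post-bronchodilator row. Table 2 also lists predicted FEV1 ("Predicted value of forced expiratory volume in the first second of expiration (L"), the FEV1/FVC ratio before and after bronchodilator ("Measured FEV1 as a ratio of measured FVC"), age ("Age in completed years") and sex. It has no row for percent predicted or for predicted FVC, and height enters only through BMI.

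The Appendix (Table S1) shows that the registry auto-calculates "Pre-bronchodilator FEV₁ (% predicted") along with the post-bronchodilator value and both FVC counterparts.

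Section 4.1 compares the Section 3.1 characteristics across the five groups, using "t-test or one-way analysis of variance (ANOVA) for continuous variables" with significance at p<0.05, and then names pairwise comparisons such as stop versus continue. Section 4.2 checks baseline balance by standardized mean difference (SMD), with 10% as the limit, and plans propensity-score matching. It does not name the variables in the propensity score.

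**The concern.** A measured volume in litres mixes airway impairment with body size, sex and age. Two groups with the same impairment but a different share of women, or a different mean age, will have different mean FEV1 and FVC. The reverse also happens: a younger or more male group can be more impaired and still show the same litres. Nothing in the Section 4.1 tests adjusts for this.

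At stake is the interpretation of Objective 1, which sets out to characterise the groups clinically. A significant FEV1 or FVC row is likely to be read as a difference in disease severity. A scale that removes most of this dependence is already in the registry, but Table 2 does not select it.

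**Working it through.** The protocol gives no lung-function mean, SD or expected group difference, so there is no figure to reproduce. The calculations below are illustrations, and every lung-function and demographic input is an assumption. Group sizes are borrowed from the earlier registry study quoted in Section 1: 2791 continued, 356 stopped, 384 switched (total 3531). They are not planned sizes for this study. Tests are taken as two-sided at 0.05.

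**A. Equal impairment, different share of women.** Assume percent predicted has mean m = 0.70 and SD s = 0.20 in both groups. Predicted FEV1 is 2.6 L in women and higher by a gap g of 0.7 to 1.1 L in men, with within-sex SD 0.45 L. One group has 60% women and the other 70%.

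- Litre difference = m × g × 0.10.
- For share p, mean predicted E = 2.6 + g(1−p), and variance V = 0.45² + g²p(1−p).
- Variance of measured FEV1 = m²V + s²E² + s²V.

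For g = 0.9:
- The difference is 0.70 × 0.9 × 0.10 = 0.063 L.
- At 60% women, E = 2.96, V = 0.397 and the variance is 0.561. At 70%, E = 2.87, V = 0.373 and the variance is 0.527. The pooled SD is 0.737 L.
- SMD = 0.063 / 0.737 = 0.085.
- Stop versus continue: SE = 0.737 × √(1/2791 + 1/356) = 0.0415, z = 1.52, chance of p<0.05 about 33%.

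| Gap g (L) | Difference (L) | SMD, litres | p<0.05, stop vs continue | p<0.05, switch vs continue |
|---|---|---|---|---|
| 0.7 | 0.049 | 0.070 | 24% | 25% |
| 0.9 | 0.063 | 0.085 | 33% | 35% |
| 1.1 | 0.077 | 0.099 | 42% | 44% |

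By construction the SMD on percent predicted is 0 in every row. With a 5-point difference in the share of women, the litre SMD is only 0.035 to 0.049.

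**B. Equal impairment, different age.** Assume predicted FEV1 at age 50 of 3.6 L (men) and 2.6 L (women), falling 0.028 L per year, residual SD 0.35 L, age SD 14 years, 60% women, mean age 52, percent predicted 72% (SD 20). A group 5 years older differs by 0.72 × 0.028 × 5 = 0.10 L. With the same variance formula the pooled SD is 0.787 L, so the SMD is 0.13. A stop-versus-continue test would reach p<0.05 about 63% of the time.

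**C. Real impairment hidden.** The reference group is as in B, and the second group has 68% predicted, 50% women and mean age 49.

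- Reference: 0.72 × (3.00 − 0.056) = 2.120 L.
- Second group: 0.68 × (3.10 + 0.028) = 2.127 L.

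The litre difference is +0.007 L (SMD 0.01, pooled SD 0.803), and the test rejects about 5% of the time. The true difference in percent predicted is 4 points, an SMD of 4/20 = 0.20.

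**D. What the other rows would show.** In A with g = 0.9, the SMD for sex is 0.10 / √((0.24 + 0.21)/2) = 0.21, and for predicted FEV1 it is 0.09 / √((0.397 + 0.373)/2) = 0.15. In B, the age SMD is 5/14 = 0.36. All exceed the corresponding litre SMD.

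**The case against.** The strongest reply has four parts.

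- **Balance.** Age, sex and predicted FEV1 are Table 2 variables and fall under the same SMD check. Step D shows that they breach the 10% limit at least as readily as litre FEV1. A reader might infer that the study matches its groups on litres and so biases the outcome comparisons. The protocol does not support that: it names no propensity-score covariates, and matching on age, sex and predicted FEV1 would remove most of the FEV1 artefact. This part stands.
- **Derivability.** FEV1 percent predicted is measured over predicted FEV1, both listed, and the FEV1/FVC ratio is not in litres. A careful reader could see a demographic pattern across these rows. This stands in part. Listing the rows does not adjust the FEV1 test, and the protocol does not say the quotient will be formed. It does not help FVC, for which neither predicted FVC nor height is listed.
- **Consequence.** Lung function is not in Table 3, does not define the use groups and is not among the eligibility criteria in Table 1. This stands and limits the severity.
- **Evidence of size.** The documents give no demographic difference between the groups, so the size of the artefact is unknown. This stands.

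None of the four answers the problem in the unadjusted Objective 1 tests.

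**Conclusion.** The point holds for Objective 1 and is minor. With FEV1 and FVC in litres and unadjusted tests, a demographic difference can be reported as a lung-function difference, or a real one can be masked. The exposure is greater for FVC than for FEV1.

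Under the assumptions above, a 10-point difference in the share of women gives 0.05 to 0.08 L and a 24% to 44% chance of p<0.05 with no difference in percent predicted. A 5-year age difference gives about 0.10 L and 63%. These figures depend on the assumed sex gap, age slope, SDs and group sizes. A sex difference of 5 to 10 points alone leaves the litre SMD at or below 0.10.

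The documents do not show bias in the exacerbation analysis or in any other outcome, and the calculations here do not claim it.

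**What to change.** Add four rows to Table 2: pre- and post-bronchodilator FEV1 percent predicted, and the same for FVC. State in Section 4.1 that these replace the litre values in the group tests. State in Section 4.2 that they are used wherever lung function enters the SMD check. Keep the litre rows as description only.

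The cost is a few lines of wording. The variables are already auto-calculated core variables in Table S1, so no new data collection is needed.
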